## VIII. DATA ANALYSIS

Baseline demographic and clinical characteristics will be examined by the PI in collaboration with [name]., Professor of Biostatistics. Measures of central tendency and variability will be estimated on each continuous measure; proportions estimated for categorical variables. Transformations will be used when distributional assumptions are not fulfilled for inferential tests. Dropouts and completers will be compared on baseline variables using Mann-Whitney or chi-square tests. Following FDA guidance for clinical trials, we will not correct our single primary outcome for multiple comparisons. We have 61 additional secondary/exploratory analyses. These will be corrected for multiple comparisons using the Bonferroni method, which yields an alpha level of 0.0008.

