### B. **Statistical Analyses Plan for Research Aims**

Each of the statistical tests below will use a two-tailed alpha-level of 0.05.

**Aim 1: Hypothesis 1a and 1b:** *CBT will be superior to MBCT in increasing daily steps over the course of 8-weeks of treatment and after 8 additional weeks of follow-up, and both forms of treatment will be superior to the Fitbit-only, control group.* The primary hypothesis, or Hypothesis 1a, is that the CBT group will do better than the MBCT group at increasing the number of daily steps. A secondary hypothesis, or Hypothesis 1b, is that the CBT and MBCT groups will do better at increasing the number of steps as measured by the FitBit over the 16-week study compared to the FitBit-only group. Since the data for Hypotheses 1a and 1b both use repeated measures on subjects, we will conduct analyses for both hypothesis using general linear mixed models that account for the covariance of observations within subjects. For both hypotheses, we will model a random intercept and slope for subjects and site and fixed effects for treatment, time, and potentially confounding covariates. The treatment by time interaction for both hypotheses will be used to assert the statistical significance of treatment effects. Canonical links will be used to correctly model the distribution of dependent variables: for count data (e.g. steps) Poisson regression

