models will be fit with the Poisson family and the log link and for normally distributed data linear regression models will be fit with the Gaussian distribution and identity link. To choose the correct model for the hypotheses, we will use the Shapiro-Wilk test to assess for normality as well as the deviance statistic, the Akaike information criterion and the Bayesian information criterion to assess the best fitting model. We will compare nested models with the likelihood ratio chi-square statistics for both hypotheses. When a treatment effect is significant for either Hypothesis 1a or 1b, we will clarify its clinical significance by computing, for each time point, effect size statistics that convey the magnitude of treatment group differences. For effect size of both hypotheses, we will use the standardized mean difference for continuous variables. Our primary analyses for Hypotheses 1a and 1b will use daily steps as measured by Fitbit (primary outcome), and then self-reported physical activity, weight, perceived stress, PHQ-9, Altman Mania Scale Scores, and Sheehan disability scores as secondary outcome measures

**Aim 2: Exploratory Aims (Phase II).** *Hypotheses:* Between treatment group effects sizes (and 95% CI) will be calculated. To supplement this, Mann-Whitney tests will compare treatment groups on medical burden (as measured by FRS) (*Hypothesis 2a*) and on improvement in symptoms (PHQ-9, ASRM) and functioning (SDS) (*Hypothesis 2b*) based on change from baseline.

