### C. Rate of Attrition

Some attrition (i.e., 20%) is expected and this can result in bias and reduce power, precision and generalizability. Consistent with the Intent to Treat principle, we will continue with the assessments for the study duration, even among those who fail to comply with the treatment.

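### Daily steps are assigned to a Poisson model with no overdispersion term, while time coding and the ranking of model-choice criteria stay open; if Poisson is kept, the primary test's false-positive rate can run from about 5% to 100%

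*Combined protocol and SAP*

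**What the plan says.** All of this is in the combined protocol and SAP, section VIII and its subsections B and C.

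- **Family for steps.** "Canonical links will be used to correctly model the distribution of dependent variables: for count data (e.g. steps) Poisson regression" runs on into "models will be fit with the Poisson family and the log link and for normally distributed data linear regression models". Steps are the plan's own example of a count. No allowance for overdispersion appears anywhere.
- **Primary test.** "The treatment by time interaction for both hypotheses will be used to assert the statistical significance of treatment effects". Hypothesis 1a (CBT against MBCT) is primary, tested two-sided at an uncorrected 0.05. Hypothesis 1b uses the same test.
- **Structure.** "we will model a random intercept and slope for subjects and site and fixed effects for treatment, time, and potentially confounding covariates". The coding of time is not given, nor whether the random slope matches the fixed time terms.
- **Choosing the model.** "we will use the Shapiro-Wilk test to assess for normality as well as the deviance statistic", followed by "the Akaike information criterion and the Bayesian information criterion to assess the best fitting model". Nested models are compared by likelihood ratio. No order of precedence is stated.
- **Transformation.** The opening paragraph of section VIII adds: "Transformations will be used when distributional assumptions are not fulfilled for inferential tests".
- **Attrition.** "Some attrition (i.e., 20%) is expected and this can result in bias and reduce power, precision and generalizability". Its timing is not given.

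**The concern.** A Poisson model fixes the variance at the mean. Daily step counts vary far more than that within a person. The random intercept and slope take up differences between people in level and trend, but not day-to-day or week-to-week noise. Any part of the time effect that the random slope does not cover is therefore tested against a standard error that is far too small.

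Whether this harms the primary test depends on two choices left open.

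1. **Time coding.** The single random slope suggests a straight line. The hypothesis separates 8 weeks of treatment from 8 of follow-up, which suggests two phases. Effect sizes are to be computed at each time point, which suggests categorical time.
2. **Precedence.** The Gaussian model is reserved for normally distributed data, a condition that Shapiro-Wilk will reject on thousands of right-skewed records. AIC and BIC, if compared across families, will reject Poisson. The listed criteria therefore point in opposite directions, and transformation is a possible third route.

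Defensible readings give a valid test, a test that nearly always rejects a true null, or a valid test that may lose power. The reading could be settled after the data are seen.

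**Working it through.** The plan gives no SD, effect size or power for steps (subsection D, headed as a power analysis, deals only with multiplicity), so there is no stated figure to reproduce.

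**Inputs from the documents:** 200 per therapy arm, 16 weeks (112 days) of step data, assessments at weeks 2, 4, 6, 8 and 16, 20% attrition, two-sided alpha 0.05.

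**Assumptions, not in the documents:** mean 4,000-7,000 steps a day; day SD 20-50% of the mean.

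**Step 1: size of the mismatch.** The Poisson SD is √mean: √4,000 = 63 and √7,000 = 84 steps. The variance-to-mean ratio is CV² × mean: 0.2² × 4,000 = 160 and 0.5² × 7,000 = 1,750, where Poisson assumes 1. In the base case (mean 6,000, CV 40%) it is 0.16 × 6,000 = 960, so a standard error resting on the Poisson variance alone is too small by √960 ≈ 31.

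**Step 2: false-positive rate with Poisson kept.** Three simulations under different assumptions:

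- **A:** 160 per arm (200 × 0.8), complete data, 16 weekly totals, gamma day noise, log-scale intercept SD 0.4 and slope SD 0.2, five mean/SD settings, 500 trials each (plus 300 further straight-line base-case trials).
- **B:** 200 per arm, 20% dropout, mean 5,000, slope SD 0.15, lag-1 correlation 0.3, within-person CV up to 0.5.
- **C:** 200 per arm, large-count approximation, day CV 0.05-0.4.

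| Time coding | A | B | C |
|---|---|---|---|
| Straight line | 4-9% | 5-6%; 7-9% on daily data (100 runs each) | 5-8% |
| Two-phase, one random slope | 86-97% | 90-98% (60 runs each) | 69-94% |
| Two-phase, matched random slopes | 5-6% | not run | 5-7% |
| Categorical weeks | 100% | 8 of 8 runs at each of CV 0.2 and 0.5 | 100% |

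In B with six categorical time points, the rate was 3.7% with no extra-Poisson variation, 50% at a CV of 0.02, 96% at 0.05 and 100% at 0.3. Overdispersion is thus the cause, and little of it is needed. With weeks 0, 8 and 16 only, the rate was 53-91% for CVs of 0.05-0.3.

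**Step 3: what the selection criteria would do.** Hypothesis 1a has 400 × 112 = 44,800 person-days. The Gaussian log-likelihood exceeded the Poisson by 72-795 per person-day, or about 3.2 to 35.6 million in total. Shapiro-Wilk rejected normality for raw days, day residuals, weekly residuals and subject means (all p < 10⁻⁹).

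**Step 4: an alternative.** A Gaussian mixed model on weekly means with clustered errors (1,100 base-case trials) gave 6.5% for straight-line, 5.3% for two-phase and 5.8% for weekly time. Single contrasts with subject-level variance (Gaussian and quasi-Poisson, 150 runs per setting) gave 4-9%. Quasi-Poisson with weekly time and no clustered errors gave 12% in 300 trials, against 8% for the clustered Gaussian model on the same trials; hence the clustered errors.

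**Step 5: power under straight-line time.** 200 per arm, day SD 40%, log-slope SD 0.1/0.2/0.3, log effect 0.048/0.070/0.094, 500 trials per cell:

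| 20% dropout spread over | Poisson | Same model, dispersion estimated |
|---|---|---|
| None | 82-85% | 83-84% |
| Weeks 8-15 | 78-79% | 79% |
| Weeks 5-15 | 59-76% | 78-80% |
| Weeks 2-15 | 17-44% | 77-79% |

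A separate approximation at slope SD 0.2 gave 85 v 85%, 80 v 84%, 70 v 81% and 32 v 79% for the four rows. By assuming almost no within-person noise, the model gives an early dropout's very noisy slope nearly the weight of a complete one. With dropout over weeks 2-15 the relative loss is 1 − 0.166/0.774 = 79% at the smallest slope SD and 1 − 0.442/0.768 = 42% at the largest.

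**The case against.** The most literal reading of a random slope with one treatment-by-time interaction is straight-line time, and there the false-positive rate stays near 5%. The reference to each time point concerns effect sizes computed after significance, not the test. Rejecting normality does not itself select Poisson: deviance, AIC and BIC are named for choosing the best-fitting model, and AIC and BIC would discard Poisson decisively. Within Poisson, the nested likelihood-ratio rule preferred matched two-phase slopes to the one-slope two-phase model by about 64,000-337,000 deviance units in six null data sets, and they also fitted better than categorical weeks with one slope. That picks a valid version.

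Most of this is correct, but none of it secures a valid test. The plan does not say that AIC or BIC overrides its own assignment of counts to Poisson. If the single random slope it names is kept, the same nested comparison prefers categorical to linear fixed time, which is the failing choice.

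Some limits stand. Skewed noise was assumed in the simulations, and the plan does not say what Shapiro-Wilk is applied to. The power figures depend on assumed slope SD, effect size and dropout timing, so they are illustrative. The transformation sentence sits in a general paragraph, so its application to the primary test is an inference. The Gaussian model is not exactly 5% in every run: without clustered errors it gave 8.0-8.5% (200 runs each).

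**Conclusion.** The concern holds and must be fixed before analysis, because it affects the sole primary test and the test of Hypothesis 1b. If Poisson is kept, the false-positive rate runs from about 5% (straight-line time, or two phases with matched random slopes) to 100% (categorical weeks). The upper end requires Poisson to survive model selection; if AIC or BIC prevails and a Gaussian model is used, the test is acceptable. The plan does not settle which of these happens. For straight-line time, the power loss ranges from none to more than half, depending on when the 20% attrition occurs.

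Step means and variability are assumptions, but the main result is not sensitive to them: with six categorical time points a within-person CV of 0.05 already gives 96%. Confidence is medium, because the result depends on which reading the analysts would adopt.

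**What to change.** For steps, delete the Poisson rule and the choice by Shapiro-Wilk, deviance, AIC and BIC. State that the general transformation rule does not apply to the primary test. Prespecify one primary model, its time coding and one named contrast.

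One suitable version is a Gaussian linear mixed model on weekly mean daily steps, with categorical weeks, an estimated residual covariance and subject-clustered (sandwich) standard errors, testing the CBT-minus-MBCT difference in change to a stated week. A negative binomial or quasi-Poisson model with subject-clustered standard errors is also acceptable; the negative binomial was not simulated here. Any other model becomes a sensitivity analysis.

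The cost is SAP wording only, with no new data or participants. The downside is that the analysis scale and time coding are fixed before the data are seen.

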### A. Primary Aims

**Aim 1: To determine if 1) web-based CBT or web-based MBCT, supported by use of Fitbit technology for self-tracking of activity, improves physical activity, and 2) How these two therapies compare to a Fitbit-only control group.**

*Hypothesis 1a:* Because CBT (compared to MBCT) is the more directive intervention, we hypothesize that CBT will be superior to MBCT in increasing daily steps over the course of 8-weeks of treatment and at follow-up.

*Hypothesis 1b:* Both forms of therapy-based treatment will be superior to the Fitbit only control group in increasing daily steps over the course of 8-weeks of treatment and at follow-up.

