Accessed through a links managed by MoodNetwork.org and Health-eHeart.org, interested participants will sign an online consent form waiver, found in a web portal hosted by the Eureka mHealth Research Platform. Eureka is a multi-tenant system (architecture in which a single instance of a software application serves multiple customers), which is housed on a HIPAA compliant Amazon cloud database. Once the participant has read and electronically signed the waiver of consent form, participants will register for Eureka and then complete a short battery of assessments to determine eligibility. The assessments will consist of 3 standard psychological assessments (The Patient Health Questionnaire [PHQ-9], the Altman Self-Rating Mania Scale [ASRM], and the Mini International Neuropsychiatric Interview [MINI], and 2 cardiac health assessments (The Duke Activity Status Index [DASI], and the International Physical Activity Questionnaire [IPAQ]). They will also be asked to complete a standard demographic form, and their medical and psychiatric histories. If they are not eligible, they will be thanked for their interest and informed that unfortunately, they are not eligible. If found eligible, they will provide their mailing address information so that we can ship them a Fitbit device. Once they receive their Fitbit device, they will return to the study portal to sync their fitbit with our system so that we can collect their step data complete a series of questionnaires, including the World Health Organization Composite International Diagnostic Interview for Bipolar Spectrum Disorders (CIDI), The Patient Health Questionnaire (PHQ-9), The Altman Self-Rating Mania Scale (ASRM), The Sheehan Disability Scale (SDS), The World Health Organization-5 Well-Being Index (WHO-5), the Self Efficacy for Exercise (SEE), the International Physical Activity Questionnaire (IPAQ), the Seattle Angina Questionnaire-7 (SAQ-7) and the Perceived Stress Scale (PSS). Once completed, participants will be randomized to CBT + Fitbit, MBCT + Fitbit, or the Fitbit-only control group. Those who are randomized to one of the two therapy-based treatment groups will be sent to a portal on MoodNetwork.org to access the interventions. Those randomized to the Fitbit-only treatment group will be brought to a page thanking them for their participation, reminding them to wear their fitbit for the next 16 weeks, and informing them that they will be emailed reminders when they need to return to the portal to complete surveys. All participants, regardless of study group, will be asked to return to Eureka in weeks 2, 4, 6, 8, and 16 to complete a battery of assessments and asked questions about adverse events that may have occurred since beginning the study (detailed in Table 1 below).

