**Table 1. Schedule of Assessments**

Weeks	0	1	2	4	6	8	16
	Pre				Mid	Post	Follow-Up
Demographics	X						
Medical/Psych Hx	X						
Mini International Neuropsychiatric Interview (MINI)	X						
World Health Organization Composite International Diagnostic Interview for Bipolar Spectrum Disorders (CIDI)		X					
Duke Activity Status Index (DASI)	X						
The Patient Health Questionnaire (PHQ-9)	X	X	X	X	X	X	X
Altman Self-Rating Mania Scale (ASRM)	X	X	X	X	X	X	X
Sheehan Disability Scale (SDS)		X		X		X	X
Well-Being Index (WHO-5)		X	X	X	X	X	X
Perceived Stress Scale (PSS)		X		X		X	X
Self Efficacy for Exercise (SEE)		X					

International Physical Activity Questionnaire (IPAQ) short form	X	X					
Cardiac Events	X	X	X	X	X	X	X
Seattle Angina Questionnaire – 7 (SAQ-7)*		X				X	X
Adverse Event Questions			X	X	X	X	X

\*The SAQ-7 will only be re-administered to those who respond affirmatively to having angina (coronary artery disease), heart attack, coronary bypass surgery coronary stent or angioplasty procedure or if participant has recurrent chest discomfort with activity that goes away within 10 minutes of rest or with nitroglycerin

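### Self-reported physical activity is a secondary outcome, but the only questionnaire that measures it is given twice before randomisation and never after

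*Combined protocol and SAP*

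**What the plan says.** Section VIII.B, Aim 1, makes Fitbit daily steps the primary outcome and then lists "self-reported physical activity, weight, perceived stress, PHQ-9, Altman Mania Scale Scores, and Sheehan disability scores as secondary outcome measures". On how effects are judged it says: "The treatment by time interaction for both hypotheses will be used to assert the statistical significance of treatment effects". Aim 1 covers the treatment period and the follow-up; Hypothesis 1a in section II.A reads "CBT will be superior to MBCT in increasing daily steps over the course of 8-weeks of treatment and at follow-up".

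Section VIII.B does not name the instrument for self-reported activity. Among the measures described in section IV.c, only the IPAQ assesses physical activity by self-report. The DASI estimates functional capacity and is given at week 0 only; the SEE measures confidence in being able to exercise and is given at week 1 only.

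In Table 1 the row "International Physical Activity Questionnaire (IPAQ) short form" is marked at weeks 0 and 1 and is blank at weeks 2, 4, 6, 8 and 16.

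The Overview in section IV gives the sequence. The IPAQ is first in the eligibility battery, then again in the battery done after the Fitbit arrives. The text continues: "Once completed, participants will be randomized to CBT + Fitbit, MBCT + Fitbit, or the Fitbit-only control group". After that, participants "will be asked to return to Eureka in weeks 2, 4, 6, 8, and 16 to complete a battery of assessments", with the content left to Table 1.

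**The concern.** An outcome can show a treatment effect only if it is measured after treatment is assigned. Here both scheduled values come before assignment, so a between-arm comparison of their change says nothing about CBT, MBCT or the Fitbit. If the analysis were run and reported as planned, a null result could be taken to mean that therapy did not alter self-reported activity, and a significant one would be a false positive. If the gap is found only at analysis, a prespecified secondary outcome has to be dropped with no way to recover the data. The trial then also loses its self-report check on the device measure.

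**Working it through.** **1. Which visits are after randomisation.** The Overview lists nine instruments in the battery completed just before randomisation: CIDI, PHQ-9, ASRM, SDS, WHO-5, SEE, IPAQ, SAQ-7 and PSS. All nine are marked at week 1 in Table 1, so the week 1 column is that battery. Table 1 has one further week 1 mark, Cardiac Events. The Adverse Event Questions start at week 2, and the Overview lists return visits only from week 2. Post-randomisation visits are therefore weeks 2, 4, 6, 8 and 16.

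**2. Scheduled post-randomisation values per participant (Table 1).**

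| Outcome | Weeks | Count |
|---|---|---|
| PHQ-9 | 2, 4, 6, 8, 16 | 5 |
| ASRM | 2, 4, 6, 8, 16 | 5 |
| PSS | 4, 8, 16 | 3 |
| SDS | 4, 8, 16 | 3 |
| IPAQ | none | 0 |

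**3. What the planned test estimates.** With two time points, the treatment-by-time term is the difference between arms in mean change:

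D = mean(Y₁ − Y₀ in CBT) − mean(Y₁ − Y₀ in MBCT).

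Both Y₀ and Y₁ are fixed before assignment, and assignment is random, so E(D) = 0 for any true treatment effect. The chance of a significant result equals alpha.

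**4. Which alpha.** Section VIII.B sets 0.05 two-sided for each test. Section VIII sets 0.0008 for the 61 secondary and exploratory analyses, and this reproduces: 0.05 / 61 = 0.00082. The chance of a significant result is thus 5% or 0.08%.

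**5. Simulation check.** Inputs: 200 per therapy arm (section III) less 20% attrition (section VIII.C), so 200 × 0.8 = 160 per arm. Assumed: within-person correlation 0.5 and a true week 8 standardised mean difference (SMD) of 0.5. In 10,000 simulated trials at alpha 0.05:

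- week 0 to week 1 change: significant in 4.8%, mean difference −0.001;
- week 1 to week 8 change: significant in 99.3%, mean difference 0.499.

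A second simulation (8,000 trials, correlation 0.6) put true effects of 0.2, 0.3 and 0.5 SD after week 1. The pre-randomisation change was significant in 5.4%, 5.0% and 4.9% of trials at 0.05, and in about 0.1% at 0.05/61.

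**6. What one week 8 value would add.** Two-sample t test on change, CBT v MBCT, 160 per arm, SD of change = √(2(1 − r)) in units of the outcome SD. For r = 0.3 this is √1.4 = 1.18; for r = 0.7 it is √0.6 = 0.77.

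| Assumed SMD | Alpha | r = 0.3 | r = 0.5 | r = 0.7 |
|---|---|---|---|---|
| 0.3 | 0.05 | 61.8% | 76.3% | 93.2% |
| 0.3 | 0.0008 | 13.5% | 24.4% | 53.2% |
| 0.5 | 0.05 | 96.5% | 99.4% | >99% |
| 0.5 | 0.0008 | 65.3% | 86.0% | 99.1% |

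The documents give neither an SMD nor a correlation for the IPAQ. These figures only indicate what a follow-up value could deliver; the finding rests on the count in step 2.

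**The case against.** - **The blank cells have a single source.** The absence of the IPAQ at weeks 8 and 16 rests on one row of Table 1, since the Overview names no instruments for the later visits. That is so. The row and its neighbours look intact, however, and the Overview separately confirms that the two marked administrations precede randomisation.
- **Week 1 might be on treatment.** The Pre label appears over week 0 only, and Cardiac Events is marked at week 1 but is not in the Overview's battery. On that reading the test would measure a very early effect, and the zero-expectation result in the working would not apply. The match of all nine instruments makes the reading unlikely. It also would not supply the week 8 and week 16 values that Aim 1 needs.
- **The IPAQ is not named as the outcome measure.** This is an inference, but no other candidate is described. If another instrument was meant, it is neither named nor scheduled, and the plan still needs correcting.
- **Nobody may actually run this test.** The analysts may notice and leave the outcome out. That is plausible, but an unreported prespecified outcome is also a poor result.
- **The power figures decide nothing.** They depend on assumed inputs, and a t test on change stands in for the planned random intercept and slope model, whose variance components cannot be identified from two values per person. Both points are accepted; the conclusion does not use the power figures.
- **Impact is limited.** Agreed: one secondary outcome is affected, and the primary outcome measures activity directly.

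**Conclusion.** The concern holds. The outcome list in section VIII.B cannot be met by the schedule in Table 1: the IPAQ yields no post-randomisation values, and its treatment-by-time test rejects at 5% or 0.08%, depending on which stated alpha applies, whatever the treatments do. This rests on two readings: that self-reported physical activity means the IPAQ, and that week 1 precedes randomisation as the Overview describes. If the second is wrong, there is one early value and still none at weeks 8 and 16.

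The documents do not show which text is in error. The IPAQ may have been meant for screening and baseline only, with the outcome list not updated. Fitbit steps, PHQ-9, ASRM, PSS and SDS are unaffected. It should be fixed, but it does not threaten the primary conclusion.

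**What to change.** Choose one, and do so before outcome data are seen by arm:

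1. Add the IPAQ short form to the week 8 and week 16 online batteries, name it in section VIII.B as the measure of self-reported activity, and state that the week 1 pre-randomisation value is the baseline.
2. If follow-up collection is not intended or no longer possible, remove self-reported activity from the secondary outcomes. If its tests are among the 61 additional analyses, which the documents do not itemise, update that count and the alpha derived from it.

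Either needs a short amendment with IRB approval, and section VII.a has the DSMB review all IRB amendments. Option 1 adds a few questions at two contacts already planned; participants already past week 8 or week 16 will have missing values there. Option 2 is a text change, at the price of losing a self-report check on the device.

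The same amendment could fill three gaps in description, which carry no weight in the verdict. Weight has no stated source or timing. FRS, the Hypothesis 2a outcome, is undefined and has no stated source or timing. The Aim 2 analysis text gives no predictor or moderator model, although section II states that aim and section III names treatment preference as a possible source of heterogeneity. For weight and FRS, supply the detail or remove the outcome; for Aim 2, specify the model or state that none is planned.

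### FRS and weight are to be compared between arms but have no scheduled measurement, and self-reported physical activity has none after randomisation

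*Combined protocol and SAP*

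**What the plan says.** Three parts of the combined protocol and SAP bear on this.

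**Planned analyses (section VIII.B).** For Aim 2 the plan states that "Mann-Whitney tests will compare treatment groups on medical burden (as measured by FRS"). That is the only endpoint given for Hypothesis 2a. The sentence goes on to the symptom scales and ends with "functioning (SDS) (*Hypothesis 2b*) based on change from baseline". For Hypotheses 1a and 1b, daily Fitbit steps are the primary outcome, followed by "self-reported physical activity, weight, perceived stress, PHQ-9, Altman Mania Scale Scores, and Sheehan disability scores as secondary outcome measures". Inference there comes from a repeated-measures mixed model: "The treatment by time interaction for both hypotheses will be used to assert the statistical significance of treatment effects".

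**Timing (section IV, Overview).** Eligible people complete a screening battery, receive the Fitbit, sync it and complete a second battery. Then: "Once completed, participants will be randomized to CBT + Fitbit, MBCT + Fitbit, or the Fitbit-only control group". They return for assessment at weeks 2, 4, 6, 8 and 16.

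**Collection (section IV.c).** The instruments are described one by one, and "Table 1. Schedule of Assessments" shows when each is given. The table has 15 rows. None is for FRS or weight, and the IPAQ row is marked at weeks 0 and 1 only.

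**The concern.** A between-arm comparison needs at least one value per participant after randomisation. A treatment-by-time test or a change score also needs a baseline value. If the schedule supplies neither, the analysis section promises results that the trial is not set up to produce.

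This matters more during the trial than afterwards, because a value not collected at week 8 or 16 cannot be recovered. At reporting, the team would have to drop pre-specified outcomes, which looks like selective reporting, or fill them from a source that was never planned. Section V mentions weight loss and lower medical burden as possible benefits to participants, so readers may well look for both.

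**Working it through.** The check is a count of scheduled measurements for each planned outcome.

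**Step 1: which assessments follow randomisation.** The nine questionnaires that the Overview places between receipt of the Fitbit and randomisation (CIDI, PHQ-9, ASRM, SDS, WHO-5, SEE, IPAQ, SAQ-7, PSS) are all marked in the week 1 column of Table 1. Weeks 0 and 1 are therefore before randomisation. The 5 assessments after it are weeks 2, 4, 6, 8 and 16.

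**Step 2: count them for each outcome named in section VIII.B.**

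| Outcome | Use in the plan | Weeks in Table 1 | After randomisation |
|---|---|---|---|
| PHQ-9 | Secondary; Hypothesis 2b | 0, 1, 2, 4, 6, 8, 16 | 5 |
| ASRM | Secondary; Hypothesis 2b | 0, 1, 2, 4, 6, 8, 16 | 5 |
| SDS | Secondary; Hypothesis 2b | 1, 4, 8, 16 | 3 |
| PSS | Secondary | 1, 4, 8, 16 | 3 |
| Self-reported activity (IPAQ) | Secondary | 0, 1 | 0 |
| Weight | Secondary | none | 0 |
| FRS | Hypothesis 2a | none | 0 |

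Six secondary outcomes are named: self-reported activity, weight, PSS, PHQ-9, ASRM and SDS. Weight is 1 of 6; with self-reported activity it is 2 of 6.

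**Step 3: look for another source.**
- *FRS* occurs once, in section VIII.B, and is not expanded.
- *Weight* as a measurement occurs only in section VIII.B. Elsewhere there is only the mention of weight loss in section V and titles in the reference list.
- *Week 0 forms.* Demographics and medical history are taken at week 0 only. A weight item within them would give no follow-up value.
- *Cardiac Events* is a two-question safety survey. It is neither a burden score nor a weight measure.
- *DASI* rests on self-reported work capacity but is given at week 0 only, so it cannot stand in for the IPAQ.
- *A row lost from Table 1*, which is split across pages, is unlikely for FRS and weight. The Overview and the instrument descriptions omit the same two measures.

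**Step 4: what the planned tests would have to work with.** FRS and weight have no scheduled post-randomisation data. The IPAQ has two values, so a treatment-by-time term could be fitted mechanically. But both values precede allocation, so the term would reflect chance imbalance and carry no information on treatment.

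**The case against.** The strongest reply is that the documents do not close off every source. Section IV says Fitbit data will be pulled through the API throughout the 16 weeks and does not limit the fields; heart rate variability and sleep are named only as extras beyond the public API. Each participant must hold a personal Fitbit account. The confidentiality section allows linkage to historical medical data in MoodNetwork and Eureka. A weight entry could exist in one of these places. This part stands, and it limits the conclusion: a reader might infer that the tests are impossible, but the documents support only that no source is scheduled. It does not remove the gap, because nothing commits the trial to collecting or using such entries.

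A reader might also infer that FRS must be deleted because a remote trial could not supply it. That assumes a meaning for the abbreviation which the documents never give. Without a definition, nobody can say what inputs it needs or whether they could be collected online.

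It can be argued that the closing reference to change from baseline applies only to Hypothesis 2b. That may be so, but comparing arms on FRS for a treatment effect still needs a value after randomisation.

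On importance, the reply is largely right. Aim 2 is labelled exploratory, its Mann-Whitney tests only supplement effect sizes, and Aim 2 in section II concerns heterogeneity of treatment effect with no mention of medical burden. Section V describes possible benefits to participants and is not a commitment to report these outcomes.

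**Conclusion.** The point holds in limited form. As scheduled, the trial would have no FRS or weight value at any of the 5 post-randomisation assessments, and no IPAQ value after week 1. The whole of exploratory Hypothesis 2a and 2 of the 6 named secondary outcomes therefore cannot be analysed as planned from the data the documents schedule. This is a conflict between the analysis section and the schedule, and more than missing detail. The primary outcome, Hypothesis 2b and the PSS comparison are unaffected.

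The conclusion rests on two readings: that Table 1 was reproduced without lost rows or marks, and that the IPAQ is the intended measure of self-reported activity, as the only general instrument of that kind described.

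A reader might go on to infer that the multiplicity threshold is wrong because tests without data are counted in it. The documents do not support that. The plan says "We have 61 additional secondary/exploratory analyses" but does not list them, so whether these tests are among the 61 is unknown. The stated alpha does follow from the count: 0.05/61 = 0.00082, which rounds to 0.0008. If 2 tests were removed it would be 0.05/59 = 0.00085, still 0.0008 when rounded; if 6 were removed, 0.05/55 = 0.00091. Both numbers removed are assumptions and the effect is negligible, so the point does not rely on it.

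**What to change.** Bring section VIII.B and Table 1 into line, measure by measure:

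- **Weight.** Add one self-reported item to the existing online battery at weeks 1, 8 and 16, or remove weight from the secondary outcomes. The drawback of adding it is that the value is self-reported.
- **FRS.** Define it, state its inputs and schedule them at baseline and follow-up, or remove Hypothesis 2a. The cost of keeping it cannot be judged until it is defined.
- **Self-reported physical activity.** Name the IPAQ short form as the measure and add it at weeks 8 and 16, or remove the outcome. Baseline values already exist at weeks 0 and 1.

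If the team means to take any of these from Fitbit accounts or linked network records, it should say so and give the field and the time window.

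Removal costs only wording. Keeping weight and the IPAQ adds one item and one short form to batteries that already run at those weeks, with no new contact. The change is useful only before participants reach week 8, and anyone already past week 1 would have no weight baseline.
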